ARTEMIS is a prospective cluster-randomized clinical trial that will evaluate whether patient copayment reduction significantly influences antiplatelet selection and long-term adherence. This study will also examine patient outcomes and the overall cost of care after AMI. After IRB approval, sites will be randomized to either the intervention or the control. Randomization will be stratified by annual site AMI volume and proportion of ticagrelor use using medians across potential sites as cut-offs for identifying high vs. low categories. Approximately 11,000 patients with STEMI or NSTEMI will be enrolled at approximately 300 hospitals.

1.1 Primary Objectives

The co-primary objectives of ARTEMIS are the following:

To determine if patient copayment reduction leads to higher long-term persistence of any P2Y₁₂ receptor inhibitor at one year after discharge.

To determine if patient copayment reduction leads to lower risk of MACE (composite of death, AMI, and stroke) at one year after discharge.

1.2 Secondary Objectives

To evaluate whether reducing patient copayments affects selection of P2Y₁₂ receptor inhibitor medication at discharge.

To assess the impact of copayment reduction on the total cost of health care for patients after AMI.

1.4 Sample Size Justification

The proposed sample size has been determined to provide adequate statistical power for the co-primary study objectives related to the copayment reduction intervention. The co-primary objective determines whether patient copayment reduction leads to greater persistence to P2Y₁₂ receptor inhibitor therapy at one year after hospital discharge. The hypothesis underlying this objective is that reducing patient copayment in a contemporary population of AMI patients will result in a significant increase in persistence to P2Y₁₂ receptor inhibitor therapy at one year, when compared with usual care. An increase of 4% in the persistence to P2Y₁₂ receptor inhibitor therapy would be considered a clinically important difference[1]. To achieve this objective with a patient-level randomization design, a sample size of 5392 patients would provide greater than 90% power with a two-sided Type I error rate of 0.05. A sample size of 4622 patients would provide greater than 85% power under the same assumptions. These power calculations are based on the assumption that the expected one-year persistence rate in the control group is 70%[1]. These calculations are based on the two group continuity corrected chi-square test statistic and assume that all observations are independently distributed. However, the sample size needs to be adjusted due to the cluster randomized design. We have applied the method described by Eldridge et al. [2] which accounts for the coefficient of variation (CV) of cluster

Statistical Analysis Plan

size and the intra-cluster correlation (ICC). Based on prior multicenter studies, we anticipate an ICC for this endpoint of approximately 0.025. Assuming a total of 300 sites randomized (1:1) with an average sample size of 36.67 patients per site and a CV of 0.65 would yield a design effect of approximately 2.28. The CV of 0.65 has been suggested by others and can be guided by providing minimum and maximum enrollment at the site level [2]. Therefore, a total sample size of 11,000 patients enrolled at 300 sites would result in an effective sample size of 4827 and be sufficient to provide between 85% and 90% power to detect an absolute 4% difference between treatment groups in the cluster randomized design.

For the one-year MACE endpoint, the underlying hypothesis is that patient copayment reduction leads to a reduction in MACE risk; this is partially due to the selection of a more potent antiplatelet agent that has been shown to reduce MACE risk in randomized clinical trials, and partially due to greater persistence of an evidence-based secondary prevention medication. For this endpoint, we have assumed a control group event rate of 12%. A clinically meaningful event reduction of 18% would yield a one-year event rate of 9.84% [3]. To achieve 80% power with a patient-level randomization, a 1:1 allocation ratio, and a two-sided Type I error rate of 0.05 would require a total of 6728 patients. Under the same assumptions, a total sample size of 7670 would provide 85% power. These sample size estimates are based on the continuity corrected chi-square test. Since the unit of randomization will be the site rather than the individual, we again need to consider the correlation of response within site and the CV on the number of patients enrolled per site. Prior multicenter studies have suggested an ICC of approximately 0.01 for the MACE endpoint [2]. A total sample size of 11,000 patients enrolled at 300 sites, assuming an ICC of 0.01 and a CV of 0.65, would yield an effective sample size of 7278 patients (Table). Therefore, the total sample size of 11,000 patients enrolled at 300 sites would be expected to provide between 80% and 85% power to detect an 18% relative reduction in MACE (12.0% vs. 9.84%).

Table: Required Sample Size for the MACE Endpoint

Sites	Total Sample Size	Average # of Patients per Site	ICC	CV	Effective Sample Size
250	10000	40	0.010	0.65	6414
250	11000	44	0.010	0.65	6808
250	12000	48	0.010	0.65	7174
250	13000	52	0.010	0.65	7516
250	14000	56	0.010	0.65	7836
250	15000	60	0.010	0.65	8137
250	16000	64	0.010	0.65	8420
250	17000	68	0.010	0.65	8686
250	18000	72	0.010	0.65	8936
300	10000	33.33	0.010	0.65	6830
300	11000	36.67	0.010	0.65	7278
300	12000	40	0.010	0.65	7698
300	13000	43.33	0.010	0.65	8092
300	14000	46.67	0.010	0.65	8466
300	15000	50	0.010	0.65	8818
300	16000	53.33	0.010	0.65	9150

Statistical Analysis Plan

300	17000	56.67	0.010	0.65	9465
300	18000	60	0.010	0.65	9764

Patient-reported persistence to antiplatelet therapy will be validated using pharmacy records that will be collected on a subset of the overall study population. The assumed standard deviation of 0.25 (for the proportion of days covered) is based on a recent randomized clinical trial to assess an intervention designed to improve adherence [4]. Assuming 1:1 randomization and a two-sided Type I error rate of 0.05, a sample size calculation based on the two-sample t-test suggests that a total sample size of 1644 patients will yield 90% and a total sample size of 2034 will yield 95% power. A random sample of 2400 patients from the 300 sites randomized with a CV of 0.25 and an ICC of 0.025 would yield a design effect of approximately 1.26. The resulting effective sample size of 2021 patients would yield approximately 95% power to detect a difference of 4% between the patient copayment reduction intervention and control groups. The target sample size of 2500 patients with pharmacy records allows for 4% missing data due to records that are not available.

2. General Considerations for Data Analysis

We will include a detailed flow diagram showing the number of participants' eligible, number of subjects randomized to Copayment Intervention and Usual Care arms, numbers of subjects lost to follow-up or excluded from analyses, and the number of subjects analyzed for the key study endpoints. Additionally, we will describe the number of clinical sites in Copayment Intervention and Usual Care arms including the mean (median, range) for key study elements by site. Key elements will include the following items: descriptions of participants, interventions, objectives, outcomes, and sample size justification; and details about the randomization procedure, factors used to stratify randomization, (lack of) blinding, statistical methods, participant flow, dates of recruitment, baseline data by individuals and by cluster, numbers analyzed, outcomes and estimation, adverse events, and a discussion. These elements are based on the CONSORT statement for cluster randomized studies [5].

After Steering Committee consensus, the randomization scheme was changed from 1:1 to 2:1 Usual Care vs. Intervention effective November 16, 2015. Randomization schema was added below as a covariate for adjustment.

All analyses will be conducted using SAS version 9.4 or higher software. All tests will be two-sided and a p-value of <0.05 will be considered statistically significant.

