2.2 Analysis Populations

The study population for primary and secondary analyses in ARTEMIS will start with all enrolled patients who survived the index MI hospitalization and did not withdraw from the study before hospital discharge. Since the intervention arm voucher provides copayment assistance for a generic (clopidogrel) or a brand (ticagrelor) P2Y₁₂ receptor inhibitor, we will conduct the primary endpoint analyses first among patients discharged on either clopidogrel or ticagrelor, and then repeat the analysis among all patients regardless of discharge P2Y₁₂ receptor inhibitor type.

2.3 Accounting for Hospital Clustering: Marginal vs. Conditional Modelling Approaches for Binary Endpoints

There are two general approaches that account for within hospital correlation in a statistical model; they are 1) marginal or population-averaged model and 2) conditional or subject-specific model. These two approaches differ in interpretation of model estimates and the way that correlation of measurements are incorporated in the model. For example, under the marginal model, the exponentiated treatment coefficient represents the odds of an average patient in the treatment group to be persistent compared to an average patient in the control group. Under the conditional random-effects model, the exponentiated treatment coefficient represents the odds of persistence for a treated person compared to the same person if they were not treated. As stated in the protocol we will use population averaged methods as our primary approach to account for hospital clustering.

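### Section 1.4 still states co-primary power for 1:1 allocation with all 11,000 enrolled patients analysed, a basis that the same SAP has since replaced

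*SAP*

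**What the plan says.** **Basis of the power figures (SAP Section 1.4).** The persistence calculation opens with "Assuming a total of 300 sites randomized (1:1) with an average sample size of 36.67 patients per site". The MACE calculation also specifies equal allocation. Both take the full 11,000 as the number analysed, and neither makes an allowance for loss. The only such allowance in Section 1.4 is 4% for missing pharmacy records. The MACE conclusion is that the sample size "would be expected to provide between 80% and 85% power to detect an 18% relative reduction in MACE (12.0% vs. 9.84"%); for persistence the stated range is 85% to 90%.

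**Allocation (SAP Section 2, repeated in Sections 3.1 and 3.2).** The SAP records that "the randomization scheme was changed from 1:1 to 2:1 Usual Care vs. Intervention effective November 16, 2015". The change was carried into the outcome model (Section 8.3.1), the propensity model (Section 8.3.2), the matching (Section 6.1) and the flow diagrams (Figures 2a and 2b). It was not carried into Section 1.4.

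**Population (SAP Section 2.2).** The analyses start from enrolled patients who "survived the index MI hospitalization and did not withdraw from the study before hospital discharge". The primary endpoint analyses are then run first in those discharged on clopidogrel or ticagrelor, and repeated in patients on any P2Y12 inhibitor.

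**The concern.** The power statement describes an allocation and an analysis set that the rest of the SAP no longer uses. Unequal allocation and a smaller analysis set both reduce power, and the margins are thin. For persistence the effective sample size is 4827, against 4622 needed for 85%. For MACE it is 7278, against 6728 needed for 80%. If a co-primary result is null, readers may rely on the stated bands to judge what the trial could have detected, and those bands were not computed for the trial as it now stands.

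**Working it through.** **Inputs, all from SAP Sections 1.4 and 2**
- Persistence: "the expected one-year persistence rate in the control group is 70"% and "An increase of 4% in the persistence to P2Y₁₂ receptor inhibitor therapy would be considered a clinically important difference", so 70% against 74%; ICC 0.025.
- MACE: 12% against 9.84%; ICC 0.01.
- 300 sites, 11,000 patients, CV of cluster size 0.65, two-sided 5% level for each endpoint.
- Test: "These calculations are based on the two group continuity corrected chi-square test statistic"; the same test is named for MACE.

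**Formulas**
- Design effect DE = 1 + [(1 + CV²)m − 1] × ICC, where m is patients per site. Effective N = N / DE.
- Let k be the ratio of intervention to control patients, p1 and p2 the control and intervention rates, and p̄ = (p1 + k·p2)/(1 + k). The uncorrected control-arm size is n′ = [1.96·√((1 + 1/k)·p̄(1 − p̄)) + z·√(p1(1 − p1) + p2(1 − p2)/k)]² / (p1 − p2)², where z is the normal quantile for the power.
- The continuity-corrected size is n = (n′/4)·[1 + √(1 + 2(1 + 1/k)/(n′·|p1 − p2|))]². Power at a given effective N comes from inverting these two formulas.

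**Reproducing the SAP**
- At 1:1 the formulas give 4622 (85%) and 5392 (90%) for persistence, and 6728 (80%) and 7670 (85%) for MACE. All four match.
- m = 11,000/300 = 36.67 and 1 + 0.65² = 1.4225.
- Persistence: DE = 1 + (1.4225 × 36.67 − 1) × 0.025 = 2.279; effective N = 4827.
- MACE: DE = 1 + (1.4225 × 36.67 − 1) × 0.01 = 1.512; effective N = 7277 (SAP: 7278).
- Power is 86.5% for persistence and 83.1% for MACE, both inside the stated bands.

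**Changing allocation and exclusions.** The ICCs, the CV and 300 sites are kept, with equal mean cluster size in both arms. The shares and exclusion rates are assumptions, because the SAP gives none.

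| Intervention share | Excluded | Persistence | MACE |
|---|---|---|---|
| 50% | 0% | 86.5% | 83.1% |
| 45% | 0% | 86.1% | 82.6% |
| 40% | 0% | 85.0% | 81.3% |
| 33.3% | 0% | 82.1% | 77.9% |
| 50% | 5% | 85.7% | 81.8% |
| 50% | 10% | 84.9% | 80.3% |
| 40% | 10% | 83.3% | 78.4% |

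With 10% excluded, m = 9,900/300 = 33, the design effects are 2.149 and 1.459, and the effective N is 4608 and 6783.

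**Break-points**
- Allocation alone: persistence falls below 85% just under a 40% intervention share, and MACE falls below 80% at about 37%.
- Exclusion alone at 1:1: persistence falls below 85% above about 9.4% excluded, and MACE falls below 80% above about 11.1%.

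**Unequal cluster sizes.** The 2:1 ratio applies to sites, not patients. Suppose one-third of sites but half of patients are in the intervention arm: 200 usual-care sites at 27.5 patients and 100 intervention sites at 55.
- Persistence: DE 1.953 (usual care) and 2.931 (intervention); effective N 2816 + 1877 = 4693; power about 84.0%.
- MACE: DE 1.381 and 1.772; effective N 3982 + 3103 = 7085; power about 81.3%.

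Multiplying the effective N by a single factor 4p(1 − p) misses this. With the patient share, p = 1/2, the factor is 1 and power stays at 86.5% and 83.1%. With the site share, p = 1/3, the factor is 0.889 and power is 82.2% and 78.4%.

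**The case against.** Section 1.4 contains no arithmetic error. It states its 1:1 assumption openly, and the later change is disclosed with its date. A reader could take the section as a record of how the trial was planned. That is fair, but the section is not labelled so, and other parts of the SAP were revised for the change.

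A reader might infer that the trial is underpowered, or that any modest imbalance or exclusion takes both endpoints below their bands. The document does not support that:
- The 2:1 scheme applies only from its effective date, and both schemes were used. A one-third site share overall is therefore the limiting case.
- At a 45% share with no exclusions both figures stay inside their bands. At 40%, MACE does too and persistence sits at its lower limit.
- The patient split may differ from the site split in either direction, and the exclusion rate is unknown.
- The primary MACE analysis is a Cox model. A check with Schoenfeld's formula at effective N 7278 gives 84.3% at 1:1 and 81.1% at full 2:1. The loss is again about 3 points, but the result stays in the band.

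The exclusion argument has a further limit. The analysis is repeated regardless of P2Y12 inhibitor type, and Section 2.1 says that data from all enrolled patients will be included. The restriction by discharge drug does not touch the repeat, although the removal of in-hospital deaths and early withdrawals does.

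It is also true that a null result is read mainly from its confidence interval, and that no model or decision rule depends on the power figure. This limits the consequence but does not make the stated bands correct for the current design.

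**Conclusion.** The point holds as a failure to update. The 85% to 90% and 80% to 85% bands are correct for 1:1 allocation with all 11,000 patients, and unsupported for the allocation and first-run population that the SAP now specifies. A shortfall is possible but not shown.

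On the plan's own chi-square basis with equal cluster sizes, the limiting one-third share alone costs about 4 points for persistence (86.5% to 82.1%) and 5 for MACE (83.1% to 77.9%). Milder departures cost less, and several stay within the bands. These figures rest on the SAP's ICCs, CV and 300 sites, ignore any effect of covariate adjustment, and use assumed shares and exclusion rates.

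**What to change.** In Section 1.4, label the existing calculation as the original planning basis: 1:1 site allocation with all enrolled patients analysed. Then add a restatement of power for both co-primary endpoints that:
- uses the number of sites and patients in each arm, and the size of the population analysed first under Section 2.2;
- keeps the stated ICCs and CV;
- computes the design effect separately for each arm and applies the unequal-allocation formula, not a single 4p(1 − p) factor.

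This costs a paragraph of SAP text. Enrolment, analysis models and significance level are untouched. The only downside is that the stated power may be somewhat less favourable.

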4.3 Medication fill using pharmacy data only

Inclusion Criteria: Patients with pharmacy data collected.

Persistence:

Using pharmacy data, we will calculate persistence using the same definition as in the primary analysis with non-persistence defined as a fill gap ≥ 30 days. Analogous to Section 3.1, we will use the LOCF method for patients who died before one year or had missing 1 year P2Y₁₂ status. Persistence at 1 year will be compared by copayment intervention using logistic regression with GEE to account for within hospital clustering and the same methods for adjustment as in the primary analysis.

Adherence:

Using pharmacy data, we will calculate the proportion of days covered. Patients with proportion of days covered $\geq 80\%$ of expected prescriptions over one year of follow-up or until death date will be considered adherent. Adherence at 1 year will be compared by copayment intervention using logistic regression with GEE to account for within hospital clustering and the same methods for adjustment as in the primary analysis.

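### The pharmacy substudy's 95% power is for a comparison of mean proportion of days covered that Section 4.3 does not plan, and the design effect of 1.26 should read 1.19

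*SAP*

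**What the plan says.** The last part of SAP Section 1.4 sizes the pharmacy-records subset, which is there to validate patient-reported persistence.

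- **Outcome and test.** "The assumed standard deviation of 0.25 (for the proportion of days covered") comes from an earlier adherence trial. The method is given as follows: "Assuming 1:1 randomization and a two-sided Type I error rate of 0.05, a sample size calculation based on the two-sample t-test".
- **Independent-patient sizes.** "a total sample size of 1644 patients will yield 90% and a total sample size of 2034 will yield 95% power".
- **Clustering.** For the 2400 patients to be sampled at random, the SAP writes: "from the 300 sites randomized with a CV of 0.25 and an ICC of 0.025 would yield a design effect of approximately 1.26".
- **Result.** An effective sample size of 2021, with "approximately 95% power to detect a difference of 4% between the patient copayment reduction intervention and control groups".

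Section 4.3 then sets out the between-arm analyses of the pharmacy data. Persistence is binary, with a fill gap of 30 days or more counted as non-persistent. Adherence is also binary, with a PDC cut at 80%: "Adherence at 1 year will be compared by copayment intervention using logistic regression with GEE". Persistence is handled by the same type of model. Section 4.3 has no comparison of mean PDC, and no table shell reports one. Tables 6 and 7 list fill persistence and fill adherence only, set against self-report.

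**The concern.** Two things do not fit.

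First, a design effect of 1.26 applied to 2400 patients does not give 2021, so at least one figure in that sentence pair is wrong.

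Second, the quantity that was powered (a difference in means) is not a quantity that the SAP tests. The only power statement for the pharmacy data is therefore attached to no planned analysis. The planned binary tests discard information and rest on different effect sizes.

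The stake is interpretation. Persistence is self-reported and the trial is not blinded, so the pharmacy data are the natural cross-check. A reader who carries 95% over to the fill endpoints could take a non-significant fill comparison as evidence against a self-reported effect, when the test had much less chance of detecting a difference of the planned size.

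**Working it through.** **Inputs from SAP Section 1.4.** 2400 patients; 300 sites, so m = 2400/300 = 8; ICC 0.025; CV 0.25; SD 0.25; difference 0.04; two-sided 0.05; 1:1 allocation. The main-trial persistence calculation uses CV 0.65, control rate 70%, a 4-point difference and a continuity-corrected chi-square test.

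**Formula.** The cited variable-cluster-size method is DE = 1 + [(1 + CV²)m − 1] × ICC, with effective N = N/DE.

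*Check on the main trial:* m = 36.67, CV 0.65 and ICC 0.025 give DE = 2.279 and 11,000/2.279 = 4827. Both match the SAP, so the formula is the one used.

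**Step 1: the t-test sizes.** With SD 0.25 and difference 0.04, t-test power is 90.0% at 1644 and 95.0% at 2034. Both reproduce.

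**Step 2: the design effect.**

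| CV | DE | Effective N | t-test power |
|---|---|---|---|
| 0.25 (stated) | 1 + (1.0625 × 8 − 1) × 0.025 = 1.1875 | 2400/1.1875 = 2021 | 94.9% |
| 0.65 (main trial) | 1 + (1.4225 × 8 − 1) × 0.025 = 1.2595 | 2400/1.2595 = 1905 | 93.7% |

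The noncentrality is 0.04/(0.25 × √(4/N)), which is 3.60 at 2021 and 3.49 at 1905. The stated CV, effective N and power agree with each other, and only 1.26 is out of line. It equals the value for CV 0.65 to two decimals. The gap in power between the two rows is 1.2 points.

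**Step 3: PDC of at least 80%.** The SAP gives no distribution or control rate, so this step assumes normal PDC with SD 0.25, a shift of 0.04, and a design effect unchanged by dichotomising. The proportion at or above 0.80 is 1 − Φ((0.80 − mean)/0.25). The test compares two proportions without continuity correction.

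| Control mean PDC | Control vs intervention | Power at N = 1905 | Power at N = 2021 |
|---|---|---|---|
| 0.70 | 34.5% vs 40.5% | 78.0% | 80.4% |
| 0.75 | 42.1% vs 48.4% | 79.3% | 81.6% |
| 0.80 | 50.0% vs 56.4% | 79.4% | 81.7% |
| 0.85 | 57.9% vs 64.1% | 78.4% | 80.7% |
| 0.90 | 65.5% vs 71.2% | 76.1% | 78.5% |

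The range is about 76–82%.

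**Step 4: fill persistence.** Section 4.3 takes over the primary definition of persistence, so the main trial's 70% vs 74% is a natural, though unstated, assumption. Under the continuity-corrected chi-square test:

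- 4622 independent patients give 85.0%, which reproduces the SAP's main-trial figure.
- Effective N 2021 gives 49.7%.
- Effective N 1905 gives 47.3%.

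The effective N is less than half of the 4622 that the SAP itself requires for 85% power at this difference.

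**The case against.** The best defence is that the stated power is sound for what it describes. The SAP's CV and ICC lead to 2021 and 94.9% without passing through 1.26, so the misprint affects no sample size, model or conclusion. This stands. A reader might infer from the mismatch that the 95% is arithmetically wrong. It is not: even if 1.26 is kept, power is 93.7%.

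A second defence is that validation of self-report does not depend on a between-arm test. Section 4.5 does it by agreement, using kappa statistics overall and by arm. This also stands, and it limits the harm to how the Section 4.3 comparisons are read. It does not explain why Section 1.4 gives power for a between-arm difference that is never tested.

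A third is that binary power rests on inputs the SAP does not give. That is fair, and two stronger readings fall with it. One is that the adherence test has only even odds of success. The 47–50% applies to fill persistence under borrowed rates; a 4-point shift in mean PDC is not a 4-point shift in the proportion above 80%. The other is that CV 0.25 is too optimistic and 0.65 must replace it. The SAP does not say how the random sample is spread across sites, so neither value can be ruled out.

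**Conclusion.** The point holds in two parts of unequal weight.

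The design effect of 1.26 is inconsistent with the inputs printed beside it; 1.19 is the matching value. This is certain, but worth at most 1.2 points of power.

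The mismatch between the powered and the planned analysis is also certain from the text, and it is the part that deserves action. The 95% supports no test in Section 4.3. Its size is conditional: about 76–82% for the 80% cut under a normal PDC with control mean 0.70–0.90, and about 47–50% for fill persistence if the main trial's rates apply. All figures keep the stated 1:1 split, use the ICC of 0.025 for the binary endpoints too, and ignore any gain from covariate adjustment. Real PDC data may be skewed, so the first range is a guide rather than an estimate.

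Nothing here shows that the binary endpoints are inappropriate or that the 80% cut should be demoted.

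**What to change.** 1. In Section 1.4, change the design effect to about 1.19. If CV 0.65 was intended, restate the whole set instead: CV 0.65, design effect 1.26, effective sample size 1905, power about 94%.
2. In Section 4.3, add a between-arm comparison of mean PDC by linear GEE clustered on hospital, with the same adjustment as the primary analysis. Name it as the analysis to which the power statement refers, and keep both binary endpoints alongside it.
3. In Section 1.4, say that the 95% does not apply to the binary fill endpoints, and give their lower power with the control rates or PDC distribution assumed.

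The cost is SAP wording, one further model on data that are already to be collected (with a row in a table shell), and a less favourable stated power for the binary endpoints.

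### Two co-primary endpoints are each tested at two-sided 0.05 with no multiplicity rule, so the chance of at least one false-positive primary claim is about 9.75% if both nulls hold

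*SAP*

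**What the plan says.** SAP Section 1.1 lists persistence with any P2Y₁₂ inhibitor and MACE, both at one year, under the line "The co-primary objectives of ARTEMIS are the following".

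Section 1.4 sizes each endpoint separately at full alpha. For persistence, "a sample size of 5392 patients would provide greater than 90% power with a two-sided Type I error rate of 0.05"; for MACE, "a 1:1 allocation ratio, and a two-sided Type I error rate of 0.05 would require a total of 6728 patients". With 11,000 patients at 300 sites it gives 85% to 90% power for persistence and 80% to 85% for MACE.

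Sections 3.1 and 3.2 give each endpoint its own primary model. The only rule for declaring a result is in Section 2: "All tests will be two-sided and a p-value of <0.05 will be considered statistically significant". No section says whether one or both endpoints must succeed, sets a testing order, divides alpha, or says that multiplicity is deliberately left unadjusted.

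Section 2.2 has the primary endpoint analyses done first in patients discharged on clopidogrel or ticagrelor, then repeated in all patients.

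**The concern.** Two primary tests of one intervention, each with its own 5% error, give two chances of a false claim. Section 1.4 attributes the expected MACE benefit partly to better persistence, so the endpoints are linked parts of one hypothesis and not two unrelated studies. Under the Section 2 rule, a mixed result (one endpoint below 0.05, the other not) would let the successful endpoint be reported as a confirmed primary finding at unadjusted alpha. The SAP does not say how such a result should be read, so that reading could be chosen after the data are seen.

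**Working it through.** **Inputs (SAP Section 1.4).** Two-sided alpha 0.05 for each endpoint; persistence 70% vs 74%; MACE 12% vs 9.84%; 11,000 patients at 300 sites (mean 36.67); CV 0.65; ICC 0.025 (persistence) and 0.01 (MACE); 1:1 allocation; continuity-corrected chi-square test.

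**Step 1: reproduce the plan's figures.** With d the difference in proportions, the uncorrected size per group is n₀ = [z₀.₉₇₅√(2p̄q̄) + z_power√(p₁q₁ + p₂q₂)]²/d². The corrected size is n = (n₀/4)[1 + √(1 + 4/(n₀d))]².

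| Endpoint | Power | Total N computed | SAP |
|---|---|---|---|
| Persistence | 90% | 5392 | 5392 |
| Persistence | 85% | 4622 | 4622 |
| MACE | 80% | 6728 | 6728 |
| MACE | 85% | 7670 | 7670 |

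Design effect = 1 + [(CV² + 1)m − 1] × ICC, where (0.4225 + 1) × 36.67 − 1 = 51.16.
- Persistence: 1 + 51.16 × 0.025 = 2.279; 11,000/2.279 = 4827 (SAP 4827).
- MACE: 1 + 51.16 × 0.01 = 1.512; effective N 7277 (SAP 7278).

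Inverting the sample-size formula at these effective sizes gives power of 86.5% for persistence and 83.1% for MACE. Both lie inside the SAP's ranges, so its single-test powers are right.

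**Step 2: error if either endpoint may be claimed.** With both nulls true and independent tests, 1 − 0.95² = 9.75%. Counting only false claims of benefit, 1 − 0.975² = 4.9% against 2.5%. The SAP gives no correlation between the test statistics, so a range is assumed (bivariate normal):

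| Correlation | Familywise error, either suffices | Joint power, both required |
|---|---|---|
| 0 | 9.75% | 0.865 × 0.831 = 71.9% |
| 0.2 | 9.6% | 73.1% |
| 0.5 | 9.1% | 75.4% |
| 0.8 | 7.8% | 78.7% |
| 1 | 5.0% | 83.1% |

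The two columns are alternatives. If either endpoint suffices, the error column applies. If both are required, type I error is controlled at 0.05 and the power column applies.

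**Step 3: cost of controlling the error.** At alpha 0.025 the same inversion gives 79.4% (persistence) and 75.0% (MACE). Holm rejects an endpoint if its p<0.025, or if its p<0.05 and the other's p<0.025. Hochberg rejects both if both are below 0.05, and otherwise one if its p<0.025. For independent tests:
- Holm, persistence: 0.794 + (0.865 − 0.794) × 0.750 = 84.8%
- Holm, MACE: 0.750 + (0.831 − 0.750) × 0.794 = 81.4%
- Hochberg, persistence: 0.794 + (0.865 − 0.794) × 0.831 = 85.3%
- Hochberg, MACE: 0.750 + (0.831 − 0.750) × 0.865 = 82.0%

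(Results use unrounded powers.) At correlation 0.5 they are 83.6% and 80.5% for Holm, and 84.5% and 81.4% for Hochberg. Familywise error under both nulls, if independent, is 1 − 0.975² = 4.9% for Holm and 4.9375% + 0.025² = 5.0% for Hochberg.

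**The case against.** The best defence is that the rule in Section 2 says when a p-value is significant, not when the trial succeeds. Section 1.1 lists two objectives and Section 1.4 gives each its own hypothesis. If the two questions are reported separately, each keeps its 5% error, and whether a familywise rate is needed is a matter of judgement. A reader may also take co-primary to mean that both must succeed, in which case nothing is inflated. The protocol is not at hand and could hold such a rule; Section 2.3 shows that the SAP does defer to the protocol on another choice.

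Part of this stands. The 9.75% depends on an either-suffices reading, on both nulls being true, and on near-independence. But the SAP argues for no separate-questions position and states no both-required condition. It fixes one significance rule for all tests without referring to a rule elsewhere. If the protocol has one, this sentence omits it.

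Two stronger readings are tempting, and the SAP does not support them.
- A reader might infer that the stated powers are overstated and the true figure is about 72%. They are not: each is given as the power for one endpoint, and each reproduces. The 72% belongs to a both-required rule that the SAP never states.
- A reader might infer that the two populations of Section 2.2 add further uncontrolled claims. That section already puts one population first and calls the other a repeat, and the 9.75% owes nothing to it.

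**Conclusion.** The point holds in this form. The SAP fixes a rule under which either co-primary endpoint can be claimed at full alpha, and that rule roughly doubles the intended 5%: 9.75% under independence, and still above 9% at correlation 0.5. The conclusion is insensitive to the assumed correlation unless it is very high.

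If the sponsor intends that both must succeed, error control is already adequate. What is then missing is that statement and its joint power: about 72% if independent, 75% at correlation 0.5, and at most 83%.

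All powers assume the 1:1 allocation used for sizing. Section 2 reports a later change to 2:1, which would lower them somewhat; the SAP does not give the numbers enrolled under each scheme, so the loss is not computed here. The familywise error figures do not depend on the allocation.

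**What to change.** In Section 2, state that a Holm or Hochberg procedure (name one) is applied to the two co-primary p-values, at a familywise two-sided 0.05. Take both p-values from the lead population of Section 2.2, patients discharged on clopidogrel or ticagrelor, and label the all-patient repeat as supportive. Limit the general p<0.05 sentence to the other tests. Holm needs no assumption about the correlation; Hochberg is slightly more powerful.

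The cost is SAP wording and about 1 to 3 power points per endpoint: persistence from about 86.5% to 84-85%, MACE from about 83% to 81-82%. No change in sample size follows from this alone.

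A fixed sequence with persistence first is an alternative that keeps full power for persistence. Its cost should be stated. A MACE claim would need both tests to succeed, so its power would be about 72% to 75% (correlation 0 to 0.5). Section 1.4 also gives MACE a route through choice of a more potent agent, so a benefit arising that way alone could not be claimed.

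If both endpoints are meant to be required, say so and give the joint power over a stated range of correlations.
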